9.6 Population Sets

In the Safety Analysis Set (SAS), the Safety Analysis Set 2 (SAS 2) and in the Solicited AEs Safety Analysis Set (SASsol), subjects are analyzed in the group they actually received (“as treated”). Based on the number of subjects receiving treatment not as randomized, selected efficacy analyses performed on the SAS “as treated” may be repeated on the SAS, analyzing subjects under the treatment they were actually randomized to.

If a subject received both the active vaccine and the placebo (i.e. at the two different vaccination timepoints or the same vaccination timepoint), subjects are analyzed in the active vaccine group for “as treated” analyses.

Following the intent-to-treat principle, in the Efficacy Sets and Per-Protocol Sets, subjects are analyzed in the group to which they were randomized (“as randomized”).

Any analyses using all randomized subjects are based on vaccination “as randomized”.

Clarifying notes regarding immunogenicity analyses: There are no analyses (tables or figures) performed on the full IS (only on the Per Protocol Immunogenicity [PPI] Set which is a subset of the IS). Listings based on the IS are displayed by actual treatment received. As described above, analyses on the PPI Set are performed “as randomized”. As correct treatment allocation is an eligibility criterion for any per protocol (PP) set in this study, “as randomized” and “as treated” are identical for PP sets.

9.6.1 Safety Analysis Sets (SAS, SAS 2, SASsol)

- The SAS includes all subjects randomized in phase 2b or 3 who received at least one dose of CVnCoV or placebo
- The SASsol includes all phase 2b subjects of the SAS with at least one diary collection indicating the occurrence or lack of occurrence of solicited AEs. See Section 10.5.2 for further details.
- The SAS 2 includes all phase 2b subjects of the SAS

9.6.2 Efficacy Analysis Set Disregarding Unblinding (EASU)

The EASU includes all subjects randomized in Phase 2b or Phase 3 who:

- Received both doses of trial vaccine according to their randomization (two doses of CVnCoV if randomized to CVnCoV or two doses of placebo if randomized to placebo).
- Had not developed a virologically-confirmed case of COVID-19 before trial entry (based on exclusion criteria 1, see Trial Protocol).
- Had not developed a virologically-confirmed case of COVID-19 (definition in Section 10.7.2) or an asymptomatic case of SARS-CoV-2 (definition in Section 10.8) before 15 days after the second vaccination.
- Had not stopped the trial before 15 days after the second vaccination.
- Were SARS-CoV-2 naïve at baseline and Visit Day 43 (based on seronegativity to N protein in the blood sample taken at baseline and Visit Day 43, see Section 10.6.1 for details).
- Did not receive an AV for preventing COVID-19 prior to 15 days after the second vaccination (See Section 10.11)

Where available the information assessed by the independent Adjudication Committee of clinicians (Section 10.7.6) is used.

9.6.3 Efficacy Analysis Set (EAS)

The EAS includes all subjects of the EASU but excluding subjects who:

- Were unblinded prior to 15 days after the second vaccination (See Section 10.11)

Where available, the information assessed by the independent Adjudication Committee of clinicians (Section 10.7.6) is used.

9.6.4 Efficacy Analysis Set for Seroconversion for N Protein Antibody (EASS)

Not further applicable.

9.6.5 Immunogenicity Subset (IS)

The IS is defined as all Phase 2b subjects from the immunogenicity cohort as indicated on the CRF (i.e. ~the first 600 subjects enrolled into each of the two age groups in Phase 2b [18-60 and ≥ 61 years of age]).

9.6.6 Per Protocol Immunogenicity (PPI) Set

The PPI Set includes all Phase 2b subjects who belong to IS and who:

- Received both doses as randomized and within the windows defined in the protocol.
- Have no important protocol deviations that are expected to impact the immunogenicity outcomes as specified in Section 12.5.
- Have not received medical treatments (such as blood products, immunoglobulin therapy or an AV) that may interfere with one or both of the proposed immunogenicity measurements.
- Have at least one blood sample collected at baseline and starting at 14 days (Visit Day 43) post-second vaccination available for analysis.

Subjects who have been tested positive for COVID-19 have their data included up to the point of a positive test result.

Subjects to be excluded from the PPI Set are identified and reviewed at the Blinded Data Review Meeting held before any formal analysis (interim or final). See Section 12.5 for further details.

9.6.7 Open-Label Set (OLS)

The OLS includes all study subjects who

- Received at least 1 dose of CVnCoV.
- Provided additional written informed consent to attend the OL phase.

This implies that, to be eligible for the OLS, participants must be ongoing study subjects at the time protocol version 4.0 is approved for their site.

Participants of the open-label phase and the OLS are to be considered synonymous.

9.6.8 Cohorts in the Open-Label Phase

All subjects who rolled over to the open-label phase are allocated to 1 of these 2 cohorts:

- Cohort A: CVnCoV-AV: OL participants who received an AV before EOT.
- Cohort B: CVnCoV only: OL participants who received no AV before EOT.

Some further clarification notes on subjects who continue in the open-label phase:

- OLS subjects who were already individually unblinded during the randomized observer-blinded phase and who received CVnCoV but – according to their concomitant medication data – did not receive an AV before implementation of Protocol version 4.0 and – according to their concomitant medication data – do not receive an AV until EOT are included in cohort B.
- OLS subjects who were already individually unblinded and – according to their concomitant medication data – either received an AV during the OL phase or already any time during the blinded study phase are included in Cohort A.
- OLS subjects who intended to receive an AV but – according to their concomitant medication data – have not received an AV before EOT are in Cohort B, irrespective of their intention recorded on the CRF.
- OLS subjects who initially intended to participate in the open-label phase without receiving an AV but – according to their concomitant medication data – nevertheless receive(d) an AV (within the open-label phase or already during the blinded study phase) are in Cohort A, irrespective of their intention recorded on the CRF.
- OLS subjects who were not individually unblinded but nevertheless received an AV in the blinded phase are included in Cohort A.

Allocation to cohorts is performed retrospectively. This means: At the time of analysis the concomitant medication data of open-label participants is checked for AV receipt. If the subject has an AV application recorded for any timepoint between first study dose and EOT the subject is eligible for Cohort A. All other open-label phase participants are allocated to Cohort B.

9.6.9 Summary of Analysis Sets to be Used per Analysis

Table 3Table 4 and Table 4Error! Reference source not found. below provide an overview on the Analysis Sets used for the analyses of each endpoint.

Table 3: Summary of Analysis Sets to be Used per Analysis - Efficacy Endpoints

ENDPOINT TYPE	ENDPOINT SHORT DESCRIPTION	ANALYSIS SET
PRIMARY EFFICACY ENDPOINT	First episodes of COVID-19 cases.	EAS
	First episodes of moderate to severe COVID-19 cases.	EAS
KEY SECONDARY EFFICACY ENDPOINT	First episodes of severe COVID-19 cases.	EAS
	“Wild type” and “Alpha” SARS-CoV-2 strains	EAS
	First episodes of COVID-19 cases in subjects ≥ 61 years of age	EAS*
OTHER SECONDARY EFFICACY ENDPOINT	First episodes of SARS-CoV-2 infection, with or without symptoms.	EAS
	BoD Scores	EAS
	First episodes of COVID-19 cases with symptom onset at any time after the first trial vaccination	SAS [#]
	Severity assessment of first episodes of COVID-19 cases	EAS
	Any strain COVID-19	EAS
	Supplemental oxygenation, mechanical ventilation, hospitalization, death (cases ≥ 15 days after second vaccination)	EAS
EXPLORATORY EFFICACY ENDPOINT	Supplemental oxygenation, mechanical ventilation, hospitalization, death (cases after first dose)	SAS
	First episodes of COVID-19 cases with symptom onset ≥ 15 days after second vaccination, regardless of baseline serostatus	SAS ^{\$}
	First episodes of COVID-19 cases with symptom onset at any time after the first vaccination, regardless of baseline serostatus	SAS

ENDPOINT TYPE	ENDPOINT SHORT DESCRIPTION	ANALYSIS SET
	Second episodes of COVID-19 cases	EAS

* RESTRICTED TO SUBJECTS ≥ 61 YEARS OF AGE

RESTRICTED TO SUBJECTS WITH NEGATIVE BASELINE SEROSTATUS

\$ RESTRICTED TO SUBJECTS WHO RECEIVED BOTH DOSES AS RANDOMIZED, DID NOT DEVELOP A COVID-19 CASE OR DISCONTINUED TRIAL PRIOR TO 15 DAYS AFTER SECOND VACCINATION

Table 4: Summary of Analysis Sets to be Used per Analysis - Safety and Immunogenicity Endpoints

ENDPOINT TYPE	ENDPOINT SHORT DESCRIPTION	ANALYSIS SET
	Occurrence, intensity and relationship of medically-attended AEs	SAS
	Occurrence, intensity and relationship of SAEs and AESIs	SAS
	Occurrence of fatal SAEs	SAS
PRIMARY SAFETY ENDPOINT^{\$}	Occurrence, intensity and duration of solicited local AEs	SASsol
	Occurrence, intensity and duration of solicited systemic AEs	SASsol
	Occurrence, intensity and relationship of unsolicited AEs	SAS 2
	Occurrence of AEs leading to vaccine withdrawal or trial discontinuation	SAS
	Serum antibodies to SARS-CoV-2 RBD of S protein	PPI
SECONDARY IMMUNOGENICITY ENDPOINT	Seroconversion to SARS-CoV-2 S RBD protein	PPI [#]
	Serum viral neutralizing antibodies to SARS-CoV-2 virus	PPI
	Seroconversion to SARS-CoV-2 virus	PPI [#]

ENDPOINT TYPE	ENDPOINT SHORT DESCRIPTION	ANALYSIS SET
EXPLORATORY IMMUNOGENICITY ENDPOINT	Frequency and functionality of SARS-CoV-2 RBD of S-specific T-cell response after ICS	PPI*
	Proportion of subjects with a detectable increase in SARS-CoV-2 RBD of S-specific T-cell response.	PPI*

RESTRICTED TO SUBJECTS SERONEGATIVE TO THE N PROTEIN AT BASELINE.
*** RESTRICTED TO SUBJECTS WITH CMI ASSESSMENTS PERFORMED**
\$ ALL SAFETY ENDPOINTS ARE ANALYSED FOR ALL SUBJECTS, IN SUBJECTS SERONEGATIVE AT BASELINE, AND IN SUBJECTS SEROPOSITIVE AT BASELINE

10.0 Conventions and Derivations

10.1 Baseline and Change from Baseline

Unless otherwise stated, baseline is defined as the last non-missing measurement at Visit 1 (Day 1), prior to administration of the first dose of trial vaccine.

Change from baseline at any post baseline timepoint is defined as:

Change from baseline = Observed Value at post baseline timepoint – Observed value at baseline.

10.2 Trial Day

Throughout this trial, trial days are defined as follows:

- Day 1 is the day of first trial vaccination.
- For days after first trial vaccination, trial day in the blinded study phase is calculated as

$$\text{Trial Day} = \text{Date of day} - \text{Date of first vaccination} + 1.$$

- For days before first trial vaccination, trial day is calculated as

$$\text{Trial Day} = \text{Date of day} - \text{Date of first vaccination}.$$

- Day 1 of the open-label phase (OL-1) and EOT Day of the open-label phase (OL-2):

The protocol defines OL-1 as Trial Day 302 (-3/+21) and OL-2 as Trial Day 393 (-0/+21) for OLS subjects.

Table 5: Replacement by OL-1 and OL-2 Visits for OLS Subjects

Site Unblinding Timepoint	Day 302 Replaced?	Clinical Visit 7/Day 393 Replaced?
By Day 302	By OL-1	By OL-2
After Day 393	No	No
After Day 302 but before Day 393	No	By OL-2

10.3 Missing Data

In general, no imputation of missing values is done except for the following:

- Imputation of missing onset date for confirmed COVID-19 cases as specified in Section 10.7.2.
- For SARS-CoV-2 RBD of S protein antibodies, and viral neutralizing antibodies, concentration values marked as below the lower limit of quantification (LLOQ) are set to 0.5*LLOQ for computation purposes.
- Imputation of (partially) missing AE start dates:
 - If start date year value is missing, the date uncertainty is too high to impute a rational date. Therefore, if year value is missing, the imputed AE start date is set to missing.
 - If start date year value is before the vaccination start date year value, then the AE started before the vaccination. Therefore:
 - If month is missing, the imputed start date is set to the mid-year point (i.e., 01JULYYYY).
 - If month is not missing, the imputed start date is set to the mid-month point (i.e., 15MONYYYY).
 - If start date year value is equal to the vaccination start date year value, the start date month needs to be compared against the vaccination start date month, to determine the imputation rule to apply. Therefore:
 - If month is missing, the imputed month and imputed day is the same as start of vaccination
 - If month is lower than vaccination start date month and start date day is missing, the imputed start date is set to the mid-month point (i.e. 15MONYYYY).
 - If month is equal to the vaccination start date month and start date day is missing, the start day is set to the start day of vaccination.
 - If month is greater than the vaccination start date month and start date day is missing, the imputed start date is set to the beginning of the month (i.e., 01MONYYYY).
 - If start date year value is greater than the vaccination start date year value, the AE started after vaccination. Therefore:
 - If month is missing, the imputed start date is set to the year start point (i.e., 01JANYYYY).
 - If start date month is not missing and start date day is missing, the imputed start date is set to the beginning of the month (i.e., 01MONYYYY).
 - If after imputation of start and resolution date (see below) a start date is after the resolution date (for example if a missing day of a start date is set to 15 and the resolution date is before the 15th of the same month and year) then the start date is set to the resolution date.
- Imputation of (partially) missing AE end dates:
 - If date of resolution is completely missing, and it is assumed that it resolved at the date of the end of the trial, the date of the end of the trial is used as the AE end date.
 - If year is present, it is assumed that it resolved on 31 December of that year (i.e., 31DECYYYY), or at the end of the trial if this is earlier and in the same year.
 - If year and month are present, it is assumed that it resolved on the last day of that month, or at the end of the trial if this is earlier and in the same month/year.
- Imputation of missing AE start times:
 - If the (recorded or imputed) AE start date is equal to the vaccination start date, then the AE start time is the time of vaccination start.
 - In all other cases, AE start time is imputed as 00:00.

If not stated otherwise, the original or incomplete data is presented in listings rather than the imputed one.

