10.5.4 Unsolicited AEs

Information on unsolicited AEs occurring on each CVnCoV/placebo vaccination day (i.e. dose 1 and 2) and the following 28 days after each CVnCoV/placebo dose are collected for Phase 2b subjects. Data is recorded in the eDiary by the subject to aid AE reporting. The investigator reviews the eDiary and records information on any AEs on the CRF.

Unsolicited AEs are assigned to first or second CVnCoV/placebo dose based on the (reported or imputed) AE date. Unsolicited AEs occurring before dose 2 are assigned to dose 1. Unsolicited AEs occurring after dose 2, are assigned to dose 2. Unsolicited AEs occurring on the day of dose 2 are assigned to either dose 1 or dose 2 as per the following rules:

- If the AE occurred on the day of dose 2 but before vaccination with dose 2, the AE is assigned to dose 1.
- If the AE occurred on the day of dose 2 but on or after vaccination with dose 2, it is assigned to dose 2.
- If the AE occurred on the day of dose 2 and it cannot be determined whether it occurred before, on or after vaccination with dose 2, it is assigned to dose 2.

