12.7.1.1 Analysis of Unsolicited AEs

The following summaries of unsolicited AEs by SOC and PT are provided, separately for AEs occurring within the first 28 days after each vaccination, within the 28 days after any vaccination, and all reported AEs (including those reported later than 28 days after any vaccination):

- Occurrence of unsolicited AEs,
- Occurrence of related unsolicited AEs,
- Occurrence of unsolicited AEs by maximum severity (mild / moderate / severe),
- Occurrence of related unsolicited AEs by maximum severity (mild / moderate / severe)

Additionally, a summary of unsolicited AEs (excluding solicited AEs) occurring within the first 28 days after each vaccination and within 28 days after any dose that have a frequency of > 5% in at least one treatment arm (on PT level) by SOC and PT is provided. The summary is repeated for all reported AEs (including those reported later than 28 days after any vaccination).

Summaries of unsolicited AEs occurring within 28 days after each vaccination and within 28 days after any vaccination are provided based on the SAS 2. Summaries of all reported unsolicited AEs (including those reported later than 28 days after any vaccination) are provided based on the SAS.

Listings of unsolicited AEs and related unsolicited AEs are produced. These listings are excluding solicited AEs and flagging treatment emergent events.

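### An AE with a missing day in the month of dose 2 is imputed against dose 1 and almost always counted under dose 1

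*SAP*

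**What the plan says.** SAP 10.3 (Missing Data) compares a partial AE start date with a single vaccination start date. The relevant branches are:

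- Same year, later month: "If month is greater than the vaccination start date month and start date day is missing", the start date becomes the 1st of that month.
- Same year, same month: "If month is equal to the vaccination start date month and start date day is missing, the start day is set to the start day", meaning the dose 1 day on this reading.
- Same year, month unknown: "If month is missing, the imputed month and imputed day is the same as start of vaccination".
- Later year (dose 1 in December, dose 2 in January): "If start date month is not missing and start date day is missing, the imputed start date is set to the beginning of the month".
- Start time: the vaccination time is used only if the AE date equals the vaccination start date. "In all other cases, AE start time is imputed as 00:00".

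No branch refers to the second vaccination. SAP 10.5.4 then allocates unsolicited AEs to a dose from the reported or imputed date: "Unsolicited AEs occurring before dose 2 are assigned to dose 1". An AE on the dose 2 day goes to dose 1 if it preceded the injection, and to dose 2 if the order cannot be determined. SAP 12.7.1.1 tabulates unsolicited AEs "separately for AEs occurring within the first 28 days after each vaccination", and 12.7.1.3 uses the same per-dose windows. SAP 8.1 puts the doses 28 days apart. Protocol 9.1.1.3 allows -3/+7 days around the second visit, so the gap can be 25 to 35 days.

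**The concern.** A rule built on the first vaccination suits the question of whether an AE is treatment emergent, which SAP 10.5.1 also judges against the first vaccination. Here the same imputed date is reused for a different question: which dose the AE follows. Dose 2 usually falls in the calendar month after dose 1, so the 1st of that month normally lies between the doses. An AE known only by its month is then placed before dose 2, whatever really happened.

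Unsolicited AEs within 28 days after each vaccination in Phase 2b are a primary safety endpoint (SAP 9.1.2). For AEs that truly follow dose 2, the error runs one way: they are taken from the dose 2 column and added to dose 1.

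**Working it through.** The documents give no figure for this point, so there is nothing to reproduce. The check applies the SAP rules to an AE with known month and year and missing day, in the calendar month of dose 2.

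**Inputs.** Imputation rules from SAP 10.3, reading the vaccination start date as dose 1; allocation from SAP 10.5.4; 28-day gap from SAP 8.1; 25-35 day range from Protocol 9.1.1.3. Assumptions: every dose 1 date in 2021 equally likely (the documents give no enrolment dates), and onset uniform.

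**Examples.**
- Doses 15 January and 12 February 2021, AE in February: dated 1 February, dose 1.
- Doses 20 December 2020 and 17 January 2021, AE in January: dated 1 January, dose 1.
- Doses 2 and 30 March 2021, AE in March: dated 2 March, dose 1.
- Doses 2 January and 6 February 2021 (35 days apart), AE in February: dated 1 February. That is 30 days after dose 1 and 5 days before dose 2, so it lies outside both 28-day windows.

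**Schedules, gap of 28 days, 365 dose 1 dates.** Dose 2 falls in a later month for 336/365 = 92.1%, where the AE is set to the 1st. The doses share a month for 29/365 = 7.9%, where it is set to the dose 1 day. With gaps of 25-35 days the shared-month share is 5.3%. Dose 2 falls on the 1st for 12/365 = 3.3%, the only schedules in which the imputed date is not before dose 2. So 353/365 = 96.7% of schedules send the AE to dose 1. Read literally, the 00:00 rule makes it 100% for unsolicited AEs, because 00:00 on the dose 2 day precedes the injection.

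**AEs truly starting on days 0-28 after dose 2.**
- Possible AE days: 365 × 29 = 10,585.
- In the dose 2 calendar month: 5,713, or 5,713/10,585 = 54.0%.
- Exempt because dose 2 was on the 1st: 12 × 29, less one day for February, = 347.
- Dated before dose 2: 5,713 − 347 = 5,366; 5,366/5,713 = 93.9%, and 5,366/10,585 = 50.7% of all day-missing dose 2 AEs.

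Dose 1 dates limited to December 2020-April 2021 (also an assumption) give 53.6%, 93.9% and 50.4%.

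**AEs the current rule places correctly.** With the same set-up, 5,348 between-dose days also fall in the dose 2 month: 5,348/(5,348 + 5,713) = 48.3% before dose 2, 51.7% on or after. With gaps of 25-35 days equally weighted and onset limited to days 0-28 after dose 1, the split is 51,781 to 62,843, so 45.2% before dose 2.

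**AEs lost from both windows.** Over gaps of 25-35 days, equally weighted and counting onset on any day between the doses, 7,623 of 121,617 affected AE days (6.3%) receive a date more than 28 days after dose 1 and before dose 2. At a gap of exactly 28 days there are none.

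**Overall size.** The share of AEs with a missing day is not given. At an assumed 1-3%, about 0.01 × 50.7% = 0.5% to 0.03 × 50.7% = 1.5% of dose 2 AEs move to dose 1.

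**The case against.** The strongest objection is that any single rule is wrong for about half of these AEs. Under uniform onset 45-48% truly began before dose 2 and are placed correctly now; a dose 2 rule would misplace them and understate dose 1. This stands, and must be stated with any change. It does not make the choice neutral. The current rule misplaces the larger share, and more if onset clusters after vaccination. It also drops some AEs from the 28-day tables and runs against 10.5.4, which resolves an unknown order on the dose 2 day in favour of dose 2.

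Second, a date branch alone could fail: an AE moved to the dose 2 date would still receive 00:00 and could be read as preceding the injection. This stands too, so the time rule must change with it.

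Third, partial dates should be rare. The eDiary serves as a memory aid for unsolicited AEs, AEs are reviewed at Days 29, 30, 43 and 57, and missing data are queried (Protocol 11.4). Safety has no formal testing, and the rule is the same in both arms. This limits the importance.

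Fourth, SAP 6.1 says version 5.0 was written by an unblinded team, and 12.7.7 keeps the existing safety analyses unchanged. A new attribution rule would be a post-unblinding change. That is a reason to show both assignments, not to leave the rule undefined.

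A reader might infer that half of all dose 2 AEs are lost. The documents do not support that: the 50.7% applies only to AEs with a missing day, whose number is unknown. Nor do they support an effect on treatment-emergent status or through-EOT totals, which do not use the dose split.

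**Conclusion.** The concern holds as a minor specification gap. With the vaccination start date read as dose 1, an AE with a missing day in the dose 2 month is allocated to dose 1 in about 97% of schedules, or all of them if the 00:00 rule is applied literally. Of such AEs that truly follow dose 2, about 94% are misallocated. The per-dose 28-day unsolicited AE tables therefore understate dose 2 and overstate dose 1. With dose 2 given late in its window, some AEs also leave the any-dose 28-day table: about 6% of those affected if all gaps from 25 to 35 days are equally likely.

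The percentages rest on uniform dosing dates and uniform onset. The absolute effect cannot be computed without the count of partial dates and is probably small. If the term was meant dose by dose, the same-month branch would already give the dose 2 day; the SAP does not say so, and that alone needs settling.

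**What to change.** In SAP 10.3:

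1. Define the vaccination start date as the date of dose 1.
2. Add a branch: if the AE month and year equal those of dose 2 and the day is missing, set the start date to the dose 2 date, unless the AE end date precedes dose 2.
3. Extend the start-time rule so that an AE imputed to the dose 2 date takes the dose 2 time, not 00:00.

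Report how many AEs in the dose 2 month lack a day, and show the per-dose 28-day tables under both assignments as a sensitivity check. State the downside alongside: some AEs that truly began before dose 2 will move to dose 2.

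The cost is a few lines of text and code, a re-run of the per-dose tables (including any already delivered), and a note that the change was made after unblinding. If the count of affected AEs is negligible, the definition and that count may be enough.

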9.1.2 Primary Safety Endpoints

All safety endpoints are analyzed in all subjects, in subjects seronegative at baseline, and in subjects seropositive at baseline

- Occurrence, intensity and relationship of medically-attended AEs collected to 6 months after the second trial vaccination in all subjects.
- Occurrence, intensity and relationship of SAEs and AESIs collected through EOT Visit in all subjects.
- Occurrence of fatal SAEs through EOT Visit in all subjects.
- Occurrence, intensity and duration of each solicited local AE within 7 days after each trial vaccination in Phase 2b subjects.

- Occurrence, intensity, and duration of each solicited systemic AE within 7 days after each trial vaccination in Phase 2b subjects.
- Occurrence, intensity and relationship of unsolicited AEs occurring within 28 days after each trial vaccination in Phase 2b subjects.
- Occurrence of AEs leading to vaccine withdrawal or trial discontinuation through to EOT Visit in all subjects.

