
 Occurrence, intensity and duration of each solicited local AE within 7 days after each trial vaccination in Phase 2b subjects. Occurrence, intensity, duration of each solicited systemic AE within 7 days after each trial vaccination in Phase 2b subjects Occurrence, intensity and relationship of unsolicited AEs occurring within 28 days after each trial vaccination in Phase 2b subjects. 	
In phase 2b subjects who received at least one dose of CVnCoV or placebo vaccine:
 
The number and percentage of subjects by group reporting:
 
 Each solicited local AE within 7 days after each trial vaccination by intensity and overall Each solicited systemic AE within 7 days after each trial vaccination by intensity, by relationship to trial vaccine and overall. At least 1 unsolicited AE, at least 1 grade 3 unsolicited AE and each

ENDPOINTS (subject level)	ESTIMANDS (population level)

 Occurrence of AEs leading to vaccine withdrawal or trial discontinuation through EOT Visit in all subjects. 	
unsolicited AE by SOC/PT occurring within 28 days after each trial vaccination and overall by causal relationship to trial vaccine and overall
 
 At least 1 AE leading to vaccine withdrawal or trial discontinuation in the year after the last trial vaccination 
The mean duration in days by group with standard deviation (SD) of solicited AEs (within the solicited period, total duration).

Key Secondary Efficacy	

 Occurrence of first episodes of virologically-confirmed (RT-PCR positive) cases of moderate to severe COVID-19 meeting the case definition for the primary efficacy analysis. 	
In naïve evaluable subjects (complying with the definition of Efficacy Analysis Set) at least 15 days following second vaccination:
 
$VE = 1 - RR$ with exact 95% CI
 
Where RR is the ratio of attack rates of COVID-19 cases per 100 person month in the CVnCoV vaccine group over the placebo group.

 Occurrence of first episodes of virologically-confirmed (RT-PCR positive) severe cases of COVID-19 meeting the case definition for the primary efficacy analysis. 	
In naïve evaluable subjects (complying with the definition of Efficacy Analysis Set) at least 15 days following second vaccination:
 
$VE = 1 - RR$ with exact 95% CI

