10.5.3 Duration and Time of Onset for Solicited AEs

Duration of solicited local and systemic AEs is defined as the number of **consecutive** days with a recorded local/systemic AE regardless of grade. For example, Fatigue with Grade 1 occurring on day 2 and 3 and day 7 is counted as two separate events with the duration 2 days and 1 day.

The duration of solicited local and systemic AEs ongoing beyond Day 8 after vaccination is defined as

$$\text{Duration} = \text{AE end date} - \text{AE start date} + 1.$$

The AE end date as recorded on the CRF is used in the above formula, except for instances where the recorded date is incomplete in which case the imputed date is used.

The time of onset (Day) of a solicited AE is defined as the day of first occurrence of the AE after the trial vaccination it was assigned to (dose 1 or dose 2, see also Section 10.5.2), regardless of the severity (Grade 1 – Grade 3). The time of onset (Day) of a Grade 3 solicited AE is defined as the first day after the trial vaccination it was assigned to (dose 1 or dose 2, see also Section 10.5.2), on which the AE was first graded as severe (Grade 3), regardless of an earlier occurrence with a lower severity.

Durations are not calculated separately for each grade but rather only for any grade >0 (no matter how often it might transition up and down between grades 1 through 3) or grade=3. Only the longest consecutive duration determined this way is displayed.

Duration and time of onset are calculated separately for events recorded after each trial vaccination.

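### Imputed end dates enter the duration of solicited reactions that outlast Day 8, so the reported mean and SD can include reaction time that nobody observed

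*SAP*

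**What the plan says.** SAP 10.3 gives three rules for AE end dates. For a wholly missing date it reads "If date of resolution is completely missing, and it is assumed that it resolved at the date of the end of the trial", and that date becomes the end date. When only the year is known, "it is assumed that it resolved on 31 December of that year". When year and month are known, "it is assumed that it resolved on the last day of that month". The two partial-date rules stop at the end of the trial if that comes first in the same year or month. Solicited AEs are not exempted.

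SAP 10.5.3 has two ways to obtain a duration. The basic one counts consecutive days with the reaction recorded and needs no end date. The second opens with "The duration of solicited local and systemic AEs ongoing beyond Day 8 after vaccination is defined as" and gives end date minus start date plus 1. It takes the end date from the CRF, "except for instances where the recorded date is incomplete in which case the imputed date is used". For each subject only the longest consecutive duration is displayed.

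SAP 9.1.2 lists among the primary safety endpoints "Occurrence, intensity and duration of each solicited local AE within 7 days after each trial vaccination in Phase 2b subjects", with a parallel entry for systemic reactions. The estimand in SAP 9.5 is "The mean duration in days by group with standard deviation (SD) of solicited AEs", and a parenthesis there names both the solicited period and the total duration.

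**The concern.** Solicited reactions are collected by diary on the day of vaccination and the next 7 days. When a reaction outlasts that window, its end date depends on the CRF. If the CRF date is partial or absent, the plan replaces an unknown with the latest date compatible with what was recorded, and then averages the result with ordinary durations of a few days. A mean and SD are very sensitive to such values.

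The SAP is more cautious elsewhere. In 10.3 an AE start date with no year is left missing because the uncertainty is judged too great, yet an end date with no information at all is filled in. Protocol 10.3.9 limits its exception for AE dates to partial ones.

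At stake is the description of how long reactions last, which is part of the reactogenicity profile. A reader of the duration tables could take imputed months for observed reactions.

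**Working it through.** The documents give no figure for this point, so there is none to reproduce. They also do not give the typical duration, the number of subjects with each reaction, or the number of incomplete end dates. Those are assumed below.

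**Step 1: length of an imputed duration, L = end date − start date + 1.**
- Month-only, onset in that month: at most 31 − 1 + 1 = 31 days.
- Year-only: depends on the calendar date of onset. An onset on 2 July gives 183 days to 31 December; an earlier onset gives more, a later one less.
- Wholly missing, with *end of trial* read as the subject's own Day 393: onset Day 2 gives 393 − 2 + 1 = 392; onset Day 30 gives 393 − 30 + 1 = 364. The visit window can add up to 21 days.

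**Step 2: effect on the mean.** Let m be the subjects with the reaction, k those with an imputed end date, and b the mean of the rest. The reported mean is [(m − k)b + kL]/m. It doubles when k/m = b/(L − b). Phase 2b has about 4,000 subjects randomised 1:1, so m is at most about 2,000 per arm.

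With b = 3 days and one imputed record (k = 1):

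| L (days) | share that doubles the mean | mean, m = 20 | m = 100 | m = 1,000 |
|---|---|---|---|---|
| 31 | 3/28 = 10.7% | 4.40 | 3.28 | 3.03 |
| 183 | 3/180 = 1.7% | 12.00 | 4.80 | 3.18 |
| 364 | 3/361 = 0.83% | 21.05 | 6.61 | 3.36 |

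For example, (99 × 3 + 364)/100 = 6.61. At L = 364 the doubling share is 2/362 = 0.55% for b = 2 and 5/359 = 1.39% for b = 5. Five records among 2,000 give (1,995 × 3 + 5 × 364)/2,000 = 3.90.

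**Step 3: effect on the SD.** Take m = 500, k = 5, b = 3, L = 364 and an assumed SD of 1.5 among the rest. The mean is 6.61, and the SD is √{[495 × (1.5² + 3.61²) + 5 × 357.39²]/500}, about 36.

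**Step 4: comparison.** If the single record in m = 100 were stopped at 8 days, the length of the diary window, the mean would be (99 × 3 + 8)/100 = 3.05.

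**Step 5: which outputs are exposed.** SAP 12.7.1.2 says no solicited-AE analyses are provided at the end-of-trial analysis. SAP Appendix 6 lists the related-systemic duration tables and all duration tables by baseline serostatus as not performed. The overall local and systemic duration tables are not on that list, so they remain exposed, including their Grade 3 part, where denominators are smaller.

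**The case against.** The strongest reply is that the extreme case may never arise. SAP 10.5.3 brings in the imputed date when the recorded one is *incomplete*. SAP 10.7.2 and 10.11 treat *incomplete* and *completely missing* as different things. Read that way, 10.5.3 covers partial dates only, and the end-of-trial rule never reaches a duration. SAP 8.5 also defines end of trial at trial level, as the last subject's Day 393 visit or discontinuation. That date did not exist when Phase 2b safety was delivered 6 weeks after the second dose (SAP 12.7.6.1). Both points stand. They make 364 to 392 days a conditional figure, but year-only dates stay exposed and the text still needs a definite reading.

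The formula is also limited to reactions ongoing beyond Day 8. The SAP does not say that a missing CRF date alone puts a diary-resolved reaction into it. A reader might infer that every missing end date becomes a duration of about a year; the documents do not support that.

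A reader might also infer that the rule makes CVnCoV look worse because more of its recipients react. That does not follow. The mean depends on the share of imputed records, not their count. One 364-day record moves a group of 20 to 21.05 days and a group of 1,000 to 3.36, so a single stray record would hurt the smaller group more. For the same reason, calling late imputation conservative for safety does not settle the matter: it lengthens placebo durations too.

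There are real mitigations. Medians, quartiles and extremes are standard output (SAP 12.0), listings show unimputed dates, missing data are queried (Protocol 11.4), and diaries are reviewed at Days 29, 43 and 57. Related Grade 3 reactions reported for more than one day prompt questioning on total duration (Protocol 9.3.3.1). No safety testing is planned. These reduce the number of affected records and make an outlier visible. They do not change the mean and SD that the estimand names.

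**Conclusion.** The point holds in a limited form. For solicited reactions ongoing beyond Day 8, the plan puts imputed end dates into a duration whose mean and SD are the estimand, with no cap, flag or sensitivity analysis. The distortion is small for month-only dates and for very common reactions. It can be large for year-only dates and, if 10.5.3 covers them, for wholly missing dates, mainly in less common reactions and Grade 3 summaries.

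The sizes rest on assumed typical durations of 2 to 5 days, assumed group sizes, and reading *end of trial* as the subject's own Day 393. On the literal trial-level reading, early enrollees would get longer values still.

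The number of incomplete end dates is not given. It therefore cannot be said that any delivered table is wrong, or that either arm is favoured.

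**What to change.** State in SAP 10.3 and 10.5.3 that imputed end dates are not used for durations of solicited AEs. For a record with a missing or partial end date, count to the last day the reaction is documented as present, by diary or site contact, and flag the value as a minimum duration. Report the number with unknown end per arm beside the median and quartiles already planned. A Kaplan-Meier summary is optional.

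Then check the delivered overall local and systemic duration tables for records with an imputed end date. Establish whether wholly missing dates were imputed and which end-of-trial date was used. Re-run the tables only if a record is affected.

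The cost is a few sentences of SAP text, one check of the solicited-AE end-date field, and at most a few re-run tables. Since no further solicited-AE analyses are planned, the check matters more than the wording.
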